# **13.2.** Pharmacokinetic Sample Shipment

The plasma samples will be transferred to the analytical laboratory after completion of the study or at mutually agreed upon time points during the clinical conduct of the study. Prior to shipment, the samples will be appropriately packed in a Styrofoam cooler containing dry ice. Sufficient dry ice will be added to ensure that the samples will remain frozen for at least 24 hours for local shipments and for at least 48 hours for remote shipments. The shipment will be accompanied by documentation containing the following information: name of the study drug product, protocol number, number of patients, and number of samples included in the shipment.

All frozen PK samples will be transferred with accompanying documentation to:

#### 13.3. Bioanalytical Methodology

For all subjects, blood samples for the determination of donepezil and 6-O-desmethyl donepezil (active metabolite of donepezil) will be collected in blood collection tubes containing di-potassium ethylenediaminetetraacetic acid (K2EDTA). Following blood collection, samples will be cooled in an ice bath and centrifuged (approximately at 3000 rpm for 7 minutes) under refrigeration at a temperature of approximately 4°C as soon as possible. Within 90 minutes of collection, plasma samples will be divided into 2 aliquots and stored in suitably labeled tubes at -20±10°C, pending assay. At the end of the study, samples will be shipped in separate shipments to the analytical laboratory for analysis. Subsequent shipments will be sent after receipt in good condition of the previous shipment at the analytical laboratory.

A validated LC/MS/MS method will be used determination to determine the content of donepezil and 6-O-desmethyl donepezil in human plasma. The current method is validated for quantitation of donepezil in human plasma over the concentration range of 0.300 ng/mL to 45.0 ng/mL. A bioanalytical method for 6-O-desmethyl donepezil in human plasma will be developed and validated.

#### 13.4. Subjects to Analyze

The PK samples from all subjects will be analyzed.

#### 14. ADHESION ASSESSMENTS AND PATCH PHOTOGRAPHY

Adhesion assessments will be assessed in person by trained CRU staff and assessments of adhesion will be based on the percentage of the total surface area of the TDS that is adhered to the skin. The CRU staff member will record the percentage based upon the actual measurement at each time point with the CRU staff member blinded to the previous recorded percentage. Tactile pressure to the TDS must not be applied during the adhesion determinations A grid overlay with boxes will be used to assist with estimating the % adhesion.

Adhesion Assessments will be performed for Treatment A and B only. Adhesion assessments and photographs will be performed every 12 hours at 12, 24, 36, 48, 60, 72, 84, 96, 108, 120, 132, 144, 156, and 168 hour following TDS application and at times that a TDS is removed at or before Early Termination. The 168-hour assessment will be conducted prior to the next TDS application, if applicable. Adhesion assessments will be performed in all periods with TDS applications.

At any time of full detachment of any TDS, the time of full detachment and its 0% adherence will

be recorded, and the 0% adhesion will be assigned to all remaining adhesion time points of the current wear period. No taping of the TDS will be allowed.

At each adhesion assessment time point, a photograph will be taken as evidence of the extent of TDS adhesion to the skin (as support of the visual observation of the adhesion percentage but not to be used for automated or photometric analysis).

Following removal of each TDS, the presence or absence of remaining adhesive residue will also be recorded.

## 14.1. Patch Detachment

If a TDS partially or fully detaches from the skin, actions to reapply a detached area of the TDS, to apply pressure to the TDS, or to reinforce TDS adhesion with the skin (e.g., taping) must be avoided throughout the study. TDS detachment must not be inappropriately inhibited (e.g., by the constant pressure applied by a person or an object such as the back of a chair).

If a TDS fully detaches from the skin, the TDS must not be reapplied, and no fresh TDS will be applied for the remainder of the intended wear period. The time of full detachment of any TDS and its 0% adherence will be recorded, and the 0% adhesion will be assigned to all remaining adhesion time points of the current wear period.

## 15. IRRITATION ASSESSMENTS/SKIN TOLERABILITY

Dermal response scores, other effects numerical scores, and the combined skin irritation score (calculated as the sum of the dermal response and other effects scores) will be summarized by post removal time point (0.5, 24, 48, 72 hours post removal). Skin irritation will be followed until skin tolerability scores are  $\leq 1$ . Separate summaries by treatment and by post removal assessment time point will be provided. Whole number scores will be used. When evaluating a dermal response, at least 25% or more of the patch area should demonstrate an observable response. When multiple observable dermal responses are present, each observable response shall represent at least 25% or more of the patch area. It is recommended when determining the percentage of patch area with an observable response, record each dermal response and determine if each one response represents at least 25% or more of the patch area.

Skin tolerability assessments will be performed prior to the TDS application and after removal of the TDS application during each period using the following scale:

#### 15.1. Tolerability Scales (Dermal Response and Other Effects)

Skin Appearance	Score
No evidence of irritation	0

Minimal erythema that is barely perceptible	1
Definite erythema that is readily visible and minimal edema or minimal papular response	2
Erythema and papules	3
Definite edema	4
Erythema, edema, and papules	5
Vesicular eruption	6
Strong reaction spreading beyond the application site	7

#### **Other Effects**

Observation	Score (Numerical Equivalent)
Slightly glazed appearance	A (0)
Markedly glazed appearance	B (1)
Glazing with peeling and cracking	C (2)
Glazing with fissures	F (3)
Film of dried serous exudates covering all or part of the TDS site	G (3)
Small petechial erosions and/or scabs	H (3)

Source: FDA Draft Guidance: Assessing the Irritation and Sensitization Potential of Transdermal and Topical Delivery Systems for ANDAs. 2018.

#### 16. DISCONTINUATION AND REPLACEMENT OF SUBJECTS

#### 16.1. Withdrawal of Subjects from the Study

A subject may be discontinued or choose to withdraw from study treatment at any time if the subject, the Investigator, or the Sponsor feels that it is not in the subject's best interest to continue. The following is a list of possible reasons for study treatment discontinuation:

• Subject withdrawal of consent.

- Subject is not compliant with study procedures.
- Adverse event that in the opinion of the Investigator would be in the best interest of the subject to discontinue study treatment.
- Protocol violation requiring discontinuation of study treatment.
- Lost to follow-up.
- Sponsor request for early termination of the study.
- Positive pregnancy test (females).
- Out-of-range vital signs, at the discretion of the Investigator. In order to ensure accuracy, out-of-range vital signs may be repeated once, at least 2 minutes after an abnormal finding.
- For other reasons (e.g., Investigator/Sponsor request, inappropriate behavior, social reasons).

If a subject is withdrawn from treatment due to an adverse event, the subject will be followed and treated by the Investigator until the abnormal parameter or symptom has resolved or stabilized.

All subjects are free to withdraw from participation at any time, for any reason, specified or unspecified, and without prejudice.

## 16.2. Withdrawal of Subjects Post-Dose Study Drug

If a subject meets withdrawal criteria post-dose during the Treatment Phase, the subject will complete, if possible, all study procedures after the current (last) administration of study drug (including PK sample collections) before starting Early Termination procedures. The subject will be withdrawn and Early Termination procedures will be completed prior to the subject's discharge from the clinic.

At the discretion of the Investigator, ensuring the safety of the subjects, any ET procedures that were already performed on the same day as part of the procedures of the current treatment phase, do not need to be repeated.

The Sponsor may be contacted if clarification is required on a case-by-case basis.

#### 16.3. Replacement of Subjects

Treated subjects who discontinue treatment or withdraw early from the study will not be replaced.

# **17. STATISTICAL METHODS**

More details of the statistical analyses will be defined in the Statistical Analysis Plan (SAP). Prior to the analysis of the final study data, a detailed SAP will be written describing all analyses that will be performed.

# **17.1.** Analysis Populations

There are 5 populations in this study:

*Randomized Population*: all subjects who signed the informed consent form and are assigned a randomization number on Day 1 of Treatment Period 1, prior to the first dose of study drug.

*Intent-to-Treat (ITT) Population*: all randomized subjects who take a least 1 dose of study drug. Demographics and baseline characteristics will be summarized for the ITT population.

*Pharmacokinetic Per-Protocol (PK-PP) Population*: all ITT subjects for a particular treatment without any major protocol deviations that could affect the pharmacokinetic endpoint for that particular treatment, who received adequate treatment to reach steady state for donepezil in the particular treatment (for example, adequate TDS wear), and who provide the plasma concentrations required to calculate the donepezil AUC0-168,SS after a particular treatment. Detailed criteria for the PK-PP Population will be listed in the SAP. Demographics and baseline characteristics will be summarized for the PK-PP Population by treatment. Data from the PK-PP Population will be used for PK data listings, with descriptive statistics, and for statistical comparison between the treatments in the Test Products and the Reference.

*Safety Population*: all randomized subjects who receive at least one dose of study drug and who have at least one safety assessment. Safety measures will be analyzed for all subjects in the Safety Population.

*Adhesion Per-Protocol (ADH-PP) Population:* The ADH-PP population will be based on the number of TDSs applied (instead of the number of subjects). All TDSs applied will be part of the ADH-PP Population except those that were intentionally removed early in the trial (e.g., because of unacceptable irritation) or from subjects who discontinued use of a TDS before the end of the 7-day wear period for reasons unrelated to adhesion (e.g., because of a protocol violation or an adverse event). Individual case reports describing any subjects/TDS who were excluded from the ADH-PP Population, and the reasons for their exclusion, will be included in the clinical study report. The ADH-PP Population will be used for the summaries and statistics of adhesion data.

# **17.2. Determination of Sample Size**

An adequate number of subjects (approximately 60 subjects) will be enrolled in the study to plan for 48 subjects to complete all study periods. This sample size was based on results of a previous steady-state study comparing 10 mg/day donepezil TDS to oral 10 mg/day donepezil (Study CL-P-15086) that showed an AUC geometric mean ratio of 1.04 and a coefficient of variation of 29.3%. The calculated sample size of 48 subjects is estimated to show at least 90% power to assess bioequivalence within the limits of 80 to 125% for the geometric mean ratio if the true expected geometric mean ratio is 1.05 (assuming a coefficient of variation of 29%) for AUC. Based on adhesion scores from previous studies with the donepezil TDS, the planned sample size of the current study should be more than adequate to demonstrate, based on a one-sided lower 95% confidence interval created with 80% power, that >80% of patches are adhered for at least 75% throughout the wear period.

# 17.3. Pharmacokinetic Analysis

## **17.3.1.** Pharmacokinetic Parameters

PK parameters will be calculated for the PP population from plasma concentrations of donepezil and 6-O-desmethyl donepezil (active metabolite) using standard, non-compartmental methods using Phoenix® WinNonlin® (Version 8.3 or higher, Certara USA, Inc., Princeton, NJ). Pharmacokinetic parameters at steady state (Week 5) will include AUC0-24,SS (daily AUC), AUC0-168,SS, Tlag, Cmax, Cmin, Cavg, Ctrough, Ctau, percent peak-to-trough fluctuation (FLUCP). After oral administration, AUC0-24,SS will be calculated and multiplied by 7 to obtain AUC0-168,SS. In some subjects, because of the lag time, the Cmax and Tmax values at steady state may be observed after removal of the TDS (past 168 hours after TDS application). Additional PK parameters will be reported (see SAP for details).

Area under the plasma concentration versus time curve will be calculated by the linear trapezoidal rule. Concentrations that are below the limit of quantification (BLQ) will be treated as zero in the data summarization and descriptive statistics. In the pharmacokinetic analysis, BLQ concentrations will be treated as zero from time zero up to the time at which the first quantifiable concentration is observed; embedded and/or terminal BLQ concentrations will be treated as "missing.

# **17.3.2.** Descriptive Statistics for Pharmacokinetics

For the plasma concentrations at each time point and for each PK parameter, parametric and nonparametric descriptive statistics will be calculated. Parametric descriptive statistics include number of subjects (n), arithmetic mean and standard deviation (SD), and percent coefficient of variation (%CV). Nonparametric descriptive statistics include minimum, Q1 (25th percentile), median, Q3 (75th percentile), and maximum. Individual plasma concentrations and PK parameters and descriptive statistics by treatment will be listed.

PK parameters of exposure (concentrations and AUCs) after the 5 mg/day TDS application will be multiplied by 2 to adjust for the lower dose (dose-normalization) before comparison to the 10 mg/day treatments.

# 17.3.3. Plasma Concentration-Time Plots

Individual subject and mean plasma concentration-time profiles will be plotted for donepezil by treatment on linear and logarithmic concentration axes.

# 17.3.4. Statistical PK Comparison between Treatments

Statistical comparison of the PK parameters of exposure (AUC0-24,SS, AUC0-168,SS, Cmax, Cmin, Ctau, percent peak-to-trough fluctuation (FLUCP).) at steady state for donepezil among the 3 treatments will be performed using an Analysis of Variance (ANOVA) model for a 3-way crossover design on the ln-transformed data with sequence, period and treatment as the fixed effects and subject within sequence as a random effect. A statistically significant difference is defined as p <0.05. Intersubject, intrasubject and total variability (coefficient of variation in percent, CV%) of the PK parameters will be reported.

PK parameters of exposure (concentrations and AUCs) after the 5 mg/day TDS application will be multiplied by 2 to adjust for the lower dose (dose-normalization) before statistical comparison to the 10 mg/day treatments.

# 17.3.5. Time to Steady State Assessment

Assessment of time to achieve steady-state will be performed by a review of weekly donepezil trough levels ( $C_{tau}$ ) at time points immediately prior to dosing on Days 15, 22, 29, and 36 in each treatment period. The univariate analysis method described by Chow and Liu for examining when steady-state is attained will be implemented using log-transformed trough plasma concentrations. Modifications to the method for Treatment Periods 2 and 3 will be explained in the SAP, to possibly adjust for the attainment of a new steady state after switching to a new treatment without a washout period after the previous treatment.

# 17.3.6. Statistical Assessment of Relative Bioavailability

To examine the relative bioavailability at steady state of the 5 and 10 mg/day TDS (Tests) relative to oral donepezil (Reference), plasma donepezil exposure as characterized by AUC0-168,SS will be assessed and compared utilizing bioequivalence criteria. The least squares geometric means (LSGM) of the PK parameters for each treatment will be reported. Point estimates and 90% Confidence Intervals (CI) for the Test to Reference ratios of geometric means will be provided. Similar bioavailability for donepezil will be concluded if the 90% CIs of the LSGMs lie within the acceptable range of 0.80 to 1.25 for AUC0-168,SS. Forest plots presenting the point estimate and 90% confidence intervals for AUC0-168,SS will be constructed for the comparisons between the 5 mg/day and 10 mg/day donepezil TDS applications (Tests) and oral Aricept® (Reference).

Since the intention of the patch is to decrease the peak-to-through fluctuations with lower Cmax after the patch application compared to daily oral Aricept dosing, rather than using the conventional bioequivalence criterion for  $C_{max}$ , it is stipulated that mean steady-state donepezil  $C_{max}$  after patch administration should remain between the steady-state  $C_{max}$  and  $C_{min}$  after daily oral Aricept® administration.

# 17.4. Adhesion Analysis

TDS adhesion score results (percentage adhesion) for each TDS strength will be summarized separately for Weeks 1 through 5 and across all wear periods (Weeks 1-5 combined) as follows:

- Summary statistics (mean, SD, minimum, Q1, median, Q3, maximum) for the mean adhesion score, where the mean adhesion score for each patch is the average of the patch adhesion scores across the entire wear period.
- Adhesion score distribution at each adhesion measurement time point post patch application (i.e., 12, 24, ..., and 168 hours).
- Average adhesion score at each adhesion measurement time point post patch application.
- Number (%) of patches that are completely detached during the 7-day wear period.
- Number (%) of patches with adhesion <50% at any adhesion measurement time point during the 7-day wear period.
- Summary of frequency of time a patch was first observed with adhesion <50% during the 7-day wear period.
- Number (%) of patches with adhesion ≥75% at all adhesion assessment time points during the 7-day wear period

To assess whether at least 80% of the TDS applied are at least 75% adhered throughout the 7-day wear period, a one-sided 95% confidence interval will be determined for the probability (p) that a randomly selected TDS maintains at least 75% adhesion throughout the entire wear period. If the 95% lower confidence limit for p is greater than 80%, acceptable TDS adhesion will be concluded. The method for the calculation of the 95% lower confidence limit and the justification of the method will be provided in the SAP.

To calculate the mean adhesion score and associated statistics, the lowest adhesion score at each time point after the baseline time point  $(t_0)$  will be carried forward to subsequent time points until a lower score is observed.

# 17.5. Subject Disposition and Demographic/Baseline Characteristics

The numbers of subjects screened, the number of subjects randomized overall (Randomized Population) and per treatment sequence group, and the number of subjects in the ITT and PP populations overall and by treatment sequence group will be listed. Differences between the number of subjects in the analysis populations will be explained. For randomized subjects who discontinue from the study, the primary reason for discontinuation will be listed and summarized by treatment after which they discontinued.

Summary statistics will be provided by treatment sequence and overall for demographic characteristics (e.g., age, sex, race, and ethnicity) and baseline characteristics (e.g., body weight, height, BMI) in the ITT and PP populations. Demographic data and baseline characteristics will be

compared among treatment sequence groups for the ITT and PP population.

## 17.6. Safety Analysis

All analyses of safety will be conducted on the Safety Population. The safety assessment will be based on adverse events, physical exams, vital signs, ECG parameters, C-SSRS, safety laboratory tests, and irritation scores (for treatments with TDS).

Adverse events will be coded in accordance with the Medical Dictionary for Regulatory Activities (MedDRA). Adverse events with new onset during the study between the initiation of study drug and 5 days after the last dose of study drug will be considered treatment-emergent (TEAEs). This will include any AE with onset prior to initiation of study drug and increased severity after the treatment initiation.

Treatment-emergent adverse events will be summarized by system organ class and preferred term, and by treatment. This will include overall incidence rates (regardless of severity and relationship to study drug), and incidence rates for moderate or severe adverse events. A summary of serious adverse events, and adverse events leading to early discontinuation from the study will be presented through data listings.

Safety laboratory tests and vital signs will be summarized by post-treatment change from baseline for each of the parameters using descriptive statistics by treatment group. Those subjects with significant laboratory abnormalities will be identified in data listings. Additional safety parameters will be summarized in data listings.

#### 17.7. Interim Analysis

No interim analysis is planned for this study.

# **18. ADVERSE EXPERIENCE REPORTING AND DOCUMENTATION**

#### **18.1.** Adverse Events

#### 18.1.1. Recording and Monitoring of Adverse Events

For the purpose of this clinical trial, all Adverse Events will be recorded and monitored for all enrolled subjects from the moment they receive the dose of study drug until they complete the study at the EOS (the Follow-Up visit or the Early Termination Visit).

#### 18.1.2. Definition

An adverse event (AE) is any untoward medical occurrence in a clinical investigation of a patient administered a pharmaceutical product and that does not necessarily have a causal relationship with the treatment. An AE is therefore any unfavorable and unintended sign (including an abnormal

laboratory finding), symptom or disease temporally associated with the administration of an investigational product, whether or not related to that investigational product. An unexpected AE is one of a type not identified in nature, severity, or frequency in the current Investigator's Brochure or of greater severity or frequency than expected based on the information in the Investigator's Brochure.

The Investigator or designee will probe, via discussion with the subject, for the occurrence of AEs during each subject visit and record the information in the site's source documents. Adverse events will be recorded in the patient CRF. Adverse events will be described by duration (start and stop dates and times), severity, outcome, treatment and relation to study drug, or if unrelated, the cause.

## 18.1.3. AE Grading

The severity of each AE will be graded by the investigator using the following categories:

Mild	Does not interfere with subject's usual function (awareness of symptoms or signs, but easily tolerated [no specific medical intervention required]).
Moderate	Interferes to some extent with subject's usual function (enough discomfort to interfere with usual activity [minimal intervention; local intervention; noninvasive intervention]).
Severe	Interferes significantly with subject's usual function (incapacity to work or to do usual activities [significant symptoms requiring hospitalization or invasive intervention]).

If there is a change in severity of an AE, only the maximum severity of the AE should be recorded.

The investigator will describe the action taken in the appropriate section of the eCRF, as follows:

- None
- Study product stopped
- Study product temporarily interrupted
- Concomitant medication
- Other, specify

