In each period wherein the treatment consists of a patch, the subjects will wear a total of 5 patches for a total of 35 days (5 weeks). The last (5th) patch in the period will be removed after the morning blood draw on Day 36 (168-hour time point after the last patch in the period). No treatment will be administered on Day 36 of the period; additional post-wear PK blood samples will be collected on Day 36 after any patch treatment. Because of the lag time of donepezil plasma concentrations after TDS application, the  $C_{max}$  and  $T_{max}$  values at steady state. in some subjects, may be observed after removal of the TDS (past 168 hours after TDS application). This is the reason why an additional day (Day 36 in each treatment period) was added to the PK sampling schedule, after TDS removal at the end of the TDS dosing interval (168 hours).

In each period (Period 2 or 3) wherein the treatment consists of oral Aricept®, the subjects will an oral dose daily for a total of 35 days (5 weeks). The last oral dose in the period will be administered on the morning of Day 35. No treatment will be administered on Day 36 of the period; a PK blood sample will be collected in the morning of Day 36 at 24 hours after the last oral dose.

In Period 1, all subjects will wear patches (Treatment A). In Periods 2 and 3, subjects will either wear patches (Treatment B) or receive once-per-day oral Aricept® (Treatment C).

- The treatment in Period 2 will start on the morning of Study Day 37 after the predose blood draw for Period 2 is collected. No treatment will be administered on Study Day 72. For the patch treatment in Period 2, the patch will be removed on Study Day 72 after the 168-hour blood sample collection.
- The treatment in Period 3 will start on the morning of Study Day 73 after the predose blood draw for Period 3 is collected. No treatment will be administered on Study Day 108. For the patch treatment in Period 3, the patch will be removed on Study Day 108 after the 168-hour blood sample collection.
- Follow-Up Visit: 5 ±2 days after the day of the last oral drug administration or last TDS removal during the Treatment Phase, subjects will enter a Follow-Up Visit to evaluate safety parameters.

There will be no washout phase between treatment periods (with the exception of Day 36 within each period to collect post-treatment PK blood samples).

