dose blood draw for Period 3 is collected. No treatment will be administered on Study Day 108. For the patch treatment in Period 3, the patch will be removed on Study Day 108 after the 168-hour blood sample collection.

• Follow-Up: 5 ±2 days after the day of the last oral drug administration or last TDS removal during the Treatment Phase, subjects will enter a Follow-Up Visit to evaluate safety parameters.

There will be no washout phase between treatment periods (with the exception of Day 36 within each period to collect post-treatment PK blood samples).

Subjects will participate in the study for up to 144 days, including up to 28 days of screening, a Treatment Phase with 3 treatment periods of 36 days each, and a 5 \pm 2 day Follow-Up Visit. Eligible subjects will stay in the research clinic for 109 days (108 overnight stays) during the Treatment Phase.

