6.11.1 Adverse Events

A treatment emergent adverse event (TEAE) is defined as:

- Any AE that has a new onset during the study between the initiation of study drug and the follow-up visit.
- Any pre-existing AE that has worsened in severity on or after the initiation of study drug till the follow-up visit.

The following rules will be used to assign a TEAE to a treatment:

- A TEAE will be assigned to the treatment received immediately before onset.
- Any TEAE reported within Period 1, Day 36, when no treatment is administered, will be attributed to the last treatment received before Day 36 began.
- If the severity of a TEAE increases in a later period the TEAE at the increased severity also will be assigned to the treatment received immediately before the increase in severity.

Page 33 of 61 Confidential

All TEAEs are defined as being definitely, probably, possibly related or unrelated to the study drug. If an AE has missing relationship it is assumed to be definitely related to the study drug for analysis purposes. Additionally, any SAE considered definitely, probably, or possibly related to the study drug will also be classified by the Sponsor as either "expected" or "unexpected" upon review by the medical monitor.

Adverse event severity will be graded as Grade 1: Mild, Grade 2: Moderate, or Grade 3: Severe or Medically Significant but not immediately life-threatening. Maximum severity will be assumed for an AE with missing severity.

All AEs will be coded using the most current version of the Medical Dictionary for Regulatory Activities (MedDRA version 23.1, updated to include activities related to COVID-19) by SOC and PT.

The following tables will be presented for AEs by treatment and overall using the Safety Population:

- Overall incidence and the number of AEs, SAEs, TEAEs leading to withdrawal.
- TEAE by system organ class and preferred term, incidence and number of events
- Treatment related TEAE by system organ class and preferred term, incidence and number of events
- Serious TEAE by system organ class and preferred term, incidence and number of events and "expected or unexpected" classification
- TEAE by system organ class and preferred term by nearest relationship to study drug, incidence and number of events
- TEAE by system organ class, preferred term and maximum severity, incidence
- TEAEs leading to early withdrawal by system organ class and preferred term, incidence

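### The protocol records only an AE's maximum severity, so the SAP rule that assigns worsening to the later treatment has no input and the peak grade falls to the treatment at onset

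*Protocol*

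**What the plan says.** **Capture.** Protocol 18.1.3 instructs the site that, when the severity of an event changes, "only the maximum severity of the AE should be recorded". Protocol 18.1.2 lists what describes an event: "Adverse events will be described by duration (start and stop dates and times), severity, outcome, treatment and relation to study drug". Neither section asks for the earlier grade or for the time at which the grade changed.

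**Analysis.** SAP 6.11.1 has two attribution rules that matter here. The first: "A TEAE will be assigned to the treatment received immediately before onset". The second: "If the severity of a TEAE increases in a later period the TEAE at the increased severity also will be assigned to the treatment" given just before the increase. The tables planned in that section, by treatment and overall, include TEAE incidence by system organ class and preferred term, and incidence by maximum severity. Protocol 17.6 also plans rates of moderate or severe events.

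**Design.** Protocol 6.1: "In Period 1, all subjects will wear patches (Treatment A). In Periods 2 and 3, subjects will either wear patches (Treatment B) or receive" oral Aricept once daily. Both later treatments are 10 mg. SAP section 1 states: "There will be no washout phase between treatment periods", apart from Day 36 of each period.

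**The concern.** The worsening rule needs three things: the grade before the increase, the grade after it, and when the increase happened. The protocol keeps the second, discards the first and does not ask for the third. This is a conflict between two written rules, not a detail left for later.

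The design gives the conflict practical weight. With almost no gap between treatments, an event can run across a switch. Protocol 6.1 explains that 5 mg comes first so that subjects can get used to cholinergic effects. An event that is mild on 5 mg and stronger on 10 mg is therefore a plausible pattern, and one that the SAP rule would capture. If the rule cannot run, the by-treatment severity tables credit that stronger event to the wrong treatment. These tables serve the safety objective.

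**Working it through.** The plan gives no figure to reproduce. The check traces the rules and then sizes the effect under a stated assumption.

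**1. Map days to treatments** (Protocol 6.1). Study Days 1–36 are A (5 mg TDS), Days 37–72 the Period 2 treatment, and Days 73–108 the Period 3 treatment. B is the 10 mg TDS and C is oral Aricept 10 mg.

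**2. Apply the SAP rules to dated grades, then to a single record that holds the onset date and the maximum grade.** The days and grades are examples.

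| Event history | Sequence | SAP rules with dated grades | Single record as the protocol implies |
|---|---|---|---|
| Mild Day 20, moderate Day 45 | B then C | A mild + B moderate | A moderate |
| Mild Day 20, moderate Day 45 | C then B | A mild + C moderate | A moderate |
| Mild Day 50, severe Day 80 | B then C | B mild + C severe | B severe |
| Mild Day 50, severe Day 80 | C then B | C mild + B severe | C severe |
| Mild Day 5, moderate Day 20 | either | A, maximum moderate | A moderate |

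Rows 1 and 2: the grade under 5 mg is too high, and the 10 mg treatment loses the event altogether. The any-grade count under 5 mg does not change, because the event is counted there either way. Rows 3 and 4: the shift is between the two 10 mg treatments, and its direction depends on the randomised sequence. Row 5: worsening within one period is attributed correctly.

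**3. Size.** The documents give no rate of events that cross a switch and worsen. Let k be the number of subjects with a Period 1 onset that worsens on the 10 mg TDS. Assume that none of them has another event at the higher grade in the same table row under either treatment. Denominators: about 60 enrolled (SAP section 4), and about 50 expected on the 10 mg TDS. The 50 is the SAP 6.12 forecast for adhesion, used here as a stand-in for the safety count.

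Change under 5 mg = +100 × k/60. Change under the 10 mg TDS = −100 × k/50.

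| k (assumed) | 5 mg TDS | 10 mg TDS |
|---|---|---|
| 1 | +1.7 points | −2.0 points |
| 2 | +3.3 | −4.0 |
| 3 | +5.0 | −6.0 |
| 6 | +10.0 | −12.0 |

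**4. Look for a repair elsewhere.** The addendum revises the TEAE window in SAP 6.11.1 but leaves the worsening rule alone. SAP section 7 reports no departures from the protocol's analysis. SAP 6.11.1 allows that a continuing event may be reported more than once, but it counts such an event once and does not require a new entry or a date when the grade rises.

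**The case against.** The strongest reply is that the eCRF and its completion guide are not in the documents. Protocol 18.1.3 does not say in so many words that there is one record per event or that it keeps the first start date, and the SAP's remark about repeat reports hints that further entries may exist. This stands as a limit on certainty. It does not remove the conflict: a site that opened a new entry at each grade would be departing from 18.1.3, and a site that followed 18.1.3 would leave the SAP rule without input.

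A second reply concerns materiality. Only events that both persist across a switch and then worsen are affected. Protocol section 3 reports that application-site events were largely mild and that titrated and untitrated regimens had comparable AE profiles. The tables are descriptive, and all AEs are listed. An addendum footnote on the COVID-19 listing also mentions a gap of 7 to 8 days between Periods 2 and 3 for some visits. All of this is fair, and it is why the size is given only as an assumed range. A listing built from the same single record would not recover the missing date, however.

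A reader might infer three stronger things that the documents do not support:
- **That the error always inflates 5 mg.** It does so only for Period 1 onsets. Later onsets move between the two 10 mg treatments.
- **That the maximum-severity rule also breaks the TEAE definition for conditions present before dosing.** AE recording starts at the first dose (Protocol 12.8 and 18.1.1), so a condition with onset before dosing has no AE record for 18.1.3 to collapse. Any difficulty there comes from the collection window.
- **That the bioequivalence result is at risk.** It uses none of these data.

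**Conclusion.** The concern holds in this limited form. Protocol 18.1.3 and SAP 6.11.1 cannot both be followed as written. With data captured as the protocol instructs, the worsening rule has no input and peak severity falls to the treatment at onset. Severity is overstated for the 5 mg TDS when a Period 1 event worsens later. When a Period 2 event worsens in Period 3, the higher grade is misplaced between the 10 mg TDS and oral Aricept. The damage is confined to the by-treatment TEAE and severity summaries.

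The size cannot be calculated from the documents. The range in the working rests on an assumed 1 to 6 affected subjects and on approximate denominators. The conclusion also rests on the eCRF following 18.1.3. The point should be fixed, but it does not threaten the primary objective.

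**What to change.** **Preferred.** Change Protocol 18.1.3, and the CRF completion instructions to match, so that each increase in severity is entered as a new AE record linked to the first, with its own start date and time and its own grade. SAP 6.11.1 can then run as written, and maximum severity can be derived within each treatment from the linked records. The cost is a sentence or two of instruction and a few extra AE rows.

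**If the data are already captured.** The addendum is dated by its title to after database lock, so this may be the case, and new wording will not recover a date that was never entered. Recover the dates of increase from source documents where they exist. Where they do not, withdraw the worsening rule from SAP 6.11.1 and add a footnote to the by-treatment severity tables saying that peak severity is attributed to the treatment at onset. The cost is some source review, or else a stated limitation on what those tables show about the 10 mg treatments.
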